#### **4.3 Rationale for choice of control drugs (comparator/placebo) or combination drugs**

The study does not include a placebo control as this would not be considered ethical in this population of pediatric asthma subjects and is not required to support the primary pharmacokinetic endpoint.

#### **4.4 Purpose and timing of interim analyses/design adaptations**

A planned interim analysis will be conducted to support decision making when 6 subjects (3 subjects from each of the 2 age strata) receiving the 75 mg dose level complete the treatment and provide the planned PK and safety data. At interim analysis, safety, as well as mean and variability of PK data of the 75 mg dose level will be assessed to have the right dose and number of subjects for the higher dose at the second stage.

For detailed information, please refer to [Section 12.7](#). Once PK data from 6 children are available, an interim analysis will be performed using non-compartmental methods and based on protocol times (e.g. preliminary PK data).

Additional interim analysis may be conducted when at least 6 subjects on high dose will complete the treatment (in case where sample size on high dose is adjusted to be more than 6 after first interim analysis) and the sample size of high dose can be refined based on emerging PK data.

The flexibility to adapt the sample size and dose of the high dose cohort based on mean and variability of PK data at the low dose will ensure that the primary endpoint of this study is met supporting pediatric dose selection for Phase III. The Phase III dose selection will apply population PK methodology and combined analysis with PK data from other age strata. The non-compartmental analysis performed in this study is considered adequate to ensure sufficiently good definition of key PK properties to inform the population PK model.

#### **4.5 Risks and benefits**

Fevipirant is a potent and highly selective oral DP2 (also referred to as CRTh2) receptor antagonist being developed as a potential therapy treatment for subjects with severe asthma. DP2 is a receptor for PGD2 which mediates the activation and migration of Th2 cells and eosinophils, some of the key inflammatory cell types in asthma. Recruitment of these cells into the lung is partly responsible for the intermittent airway obstruction which leads to wheezing and shortness of breath characteristic of asthma.

Fevipirant is at least 300-fold selective for the DP2 receptor compared to other available prostanoid receptors and to cyclooxygenase-1 and cyclooxygenase-2, and it has been demonstrated to be a potent *in vitro* inhibitor of human whole blood eosinophil activation and induction of Th2 cytokines. After oral dosing in rats, QAW039 inhibited pulmonary eosinophilia induced by the PGD2 metabolite DK-PGD2.

The potential benefits of QAW039 therapy need to be balanced against its potential risks. The risk to subjects in this study will be minimized by compliance with the inclusion/exclusion criteria and close clinical monitoring. All subjects will remain on the background SoC asthma therapy they were taking at screening throughout the study, with exemption of LTRAs (LTRAs have to be stopped but in that case ICS can be initiated or dosed higher in case the subject was already on ICS). Furthermore, subjects will be instructed how to react to worsening of asthma symptoms so subjects can be managed appropriately.

Appropriate eligibility criteria and specific dose-limiting toxicity definitions, as well as specific dose modification and stopping rules, are included in this protocol.

All assessments in this trial are relatively small and part of regular medical assessments in this subject population. Procedural risks are related to blood sampling for safety and PK laboratory analyses: puncturing of the veins can cause discomfort, pain, hematoma or in rare cases lead to an infection.

The overall clinical experience with fevipirant includes 24 studies: 15 (nine in healthy volunteers and six in patients) have completed and nine (five in asthma subjects, 2 in healthy volunteers and 2 in subjects with renal or hepatic impairment) are ongoing. The completed Phase II studies consist of four in subjects with asthma, one in subjects with allergic rhinitis and

one in subjects with atopic dermatitis (AD). Five Phase III studies ( [CQAW039A2307], [CQAW039A2314], [CQAW039A2315], [CQAW039A2316] and [CQAW039A2317]) in asthma and four Phase I studies in healthy volunteers ( [CQAW039A2114] and [CQAW039A2120] </intref>) and subjects with renal or hepatic impairment ( [CQAW039A2107] and [CQAW039A2108]) are ongoing. For detailed information on the 15 completed studies, please refer to Section 5 and Section 5.2.1.2 of the [Investigator's Brochure (IB)].

As of January 2018, over 2830 subjects have been exposed to fevipiprant in the clinical program. In the completed and ongoing studies of fevipiprant, approximately 2835 subjects (420 healthy volunteers and 2415 subjects with asthma, allergic rhinitis, or atopic dermatitis) received fevipiprant, approximately 1045 subjects received placebo, and approximately 420 received other treatments (rosuvastatin, simvastatin, montelukast, fluticasone, or probenecid). Fevipiprant has been well tolerated in populations studied to date at total daily doses up to 500 mg given for durations of up to 12 weeks and at a total daily dose up to 1800 mg for a duration of up to 1 week. In the four completed studies in the asthma program, 21 subjects reported 21 serious adverse events (SAEs), no deaths due to SAEs were reported, and seven discontinuations due to SAEs were reported. Of the 21 subjects reporting SAEs, 15 subjects reported 15 events, five subjects reported five events, and one subject reported one event in the fevipiprant, placebo, and montelukast treatment groups, respectively. In the one study completed in the atopic dermatitis program, five subjects (one on fevipiprant and four on placebo) experienced a total of 6 SAEs (one in the fevipiprant group in the follow-up period, and 5 in the placebo group with 3 of them occurring during the treatment period). There were no SAEs in either program (including fatal events) with a suspected causal relationship to fevipiprant. There have been no adverse events (AEs) of idiosyncratic drug reactions.

Overall, the safety profile of fevipiprant has been favorable across studies.

## 5 Population

- At least 12 but not more than 24 male and female children  $\geq 6$  years and  $< 12$  years diagnosed with asthma.
- Six subjects will be included in Cohort A and 6 to 18 subjects in Cohort B.
- It is anticipated that approximately 20 subjects will need to be screened in order to include 12 subjects into the treatment period (screen failure rate  $\sim 40\%$ ). After the interim analysis, additional subjects may need to be recruited so that total number of subjects completing treatment is maximum 24, in this case approximately 40 subjects will need to be screened.
- It is intended that 12 to 24 patients will complete the study. Dropouts, non-completers and patients who are not eligible for PK assessment at EOT (e.g. because they did not take study drug for 3 consecutive days prior to EOT Visit) will be replaced.

Subjects will be stratified approximately 1:1 ratio into 2 age groups; 6 to  $< 9$  years and 9 to  $< 12$  years to ensure approximately equal allocation of subjects throughout the whole age range being studied.

### 5.1 Inclusion criteria

Subjects eligible for inclusion in this study must meet **all** of the following criteria:

1. Male and female children  $\geq 6$  years and  $<12$  years.
2. Written informed consent by parent(s)/legal guardian(s) for the pediatric patient and assent by the pediatric patient (depending on local requirements) must be obtained before any study-specific assessment is performed.
3. Confirmed/documented diagnosis of asthma, as defined by national or international asthma guidelines for at least 6 months prior to study enrollment.
4. Subjects using asthma rescue medication (e.g. SABA) without asthma controller therapy or patients receiving daily treatment with a stable dose ICS (with or without additional controller such as long-acting  $\beta$ -agonists (LABA), long-acting muscarinic antagonists (LAMA)) for at least 4 weeks prior to Treatment Visit (Day 1).
5. Subjects must be able to attend study visits as per Study Visit Assessment Schedule (Section 8) which includes 8 to 9 hours in the clinic/home on the day of End of Treatment Visit and have blood draws as scheduled in the study.
6. Parents/legal guardian must be willing and able to attend study visits and assist the child with the procedures outlined in the protocol (e.g. compliance with taking study medication and completing the diary).

## 5.2 Exclusion criteria

Subjects meeting any of the following criteria are not eligible for inclusion in this study.

1. Use of other investigational drugs within 5 half-lives of enrollment, or (within 30 days (for small molecules)/until the expected pharmacodynamic effect has returned to baseline (for biologics)), whichever is longer.
2. Subject is unable to ingest banana and/or yogurt
3. History of hypersensitivity to any of the study drugs or its excipients or to drugs of similar chemical classes.
4. History of chronic lung disease other than asthma such as and not limited to, sarcoidosis interstitial lung disease, cystic fibrosis, mycobacterial or other infection (including active tuberculosis or atypical mycobacterial disease).
5. History of active bacterial, viral or fungal infection within 6 weeks of Treatment Visit (Day 1).
6. Subjects who, in the opinion of the investigator, are not able to be compliant with study treatment or who have any medical or mental disorder, situation, or diagnosis, which could interfere with the proper completion of the protocol requirements or risk the subject's safety while participating in the study.
7. Parent/guardian who, in the opinion of the investigator, has a history of psychiatric disease, intellectual deficiency, substance abuse, or other condition (e.g. inability to read, comprehend and write) which will limit the validity of consent for their child to participate in this study.
8. Hemoglobin levels outside normal ranges at screening.
9. Any surgical or medical condition which might significantly alter the absorption, distribution, metabolism, or excretion of drugs, or which may jeopardize the subject in case of participation in the study.

10. Subjects who have a clinically significant ECG abnormality or clinically significant abnormal lab values reported at Screening Visit.
11. Subjects with a history of long QT syndrome or whose corrected QT interval (QTc) measured at Screening Visit (Fridericia method) is prolonged ( $\geq 450$  msec for boys and girls).
12. Subjects receiving any medications in the classes specified in [Table 6-3](#) unless they undergo the required washout period prior to Treatment Visit (Day 1) and follow the adjustment through the treatment period.
13. Subjects receiving medications in the classes listed in [Table 6-2](#) should be excluded unless the medication has been stabilized for the specified period and the stated conditions have been met.
14. History of malignancy of any organ system, treated or untreated, within the past 5 years, regardless of whether there is evidence of local recurrence or metastases.
15. Subject is an immediate family member of the participating investigator, sub-investigator, study coordinator, or employee of the participating investigator.
16. History or presence of impaired renal function as indicated by clinically significantly abnormal creatinine or blood urea nitrogen (BUN) and/or urea values, or abnormal urinary constituents (e.g. albuminuria) according to investigator's judgement.
17. Pregnant or nursing (lactating) females ([Section 8.4.3](#)).

No additional exclusions may be applied by the investigator, in order to ensure that the study population will be representative of all eligible subjects.

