### **Screening Period (Screening to Treatment Visit)**

Within 14 days prior to treatment visit or at Screening Visit, written informed consent from the parent(s)/legal guardian(s), and subject assent (if applicable), will be obtained before any study-related assessments or procedures are performed. The subject's participation in the trial must be documented in the subject's medical record and all study related evaluations performed at each visit must be clearly documented in source documentation and on electronic case report forms (eCRFs).

Study sites should check the interactive response technology (IRT) for subject age cohort availability before Screening Visit begins. If the subject qualifies, Screening Visit can proceed with the documentation of demographic data, the assessment of study inclusion/exclusion criteria, and past/current medical history. The subject can then be entered into the IRT system to continue screening.

Once IRT has confirmed subject participation, physical and laboratory assessments may be performed ( [Section 8.4](#) ). At this visit, subjects will be instructed to withhold any prohibited medication as applicable ( [Table 6-3](#) ) prior to Treatment Visit (Day 1). The window between Screening Visit and Treatment Visit Day 1 (Screening Period) is up to 14 days.

Throughout the study (from Screening Visit through Follow-up period), subjects will continue to receive their rescue medication (e.g. SABA) and potentially SoC asthma therapy which could be ICS with or without additional controller medication. Leukotriene receptor-antagonists (LTRAs) must be stopped at Screening Visit and in that case ICS should be initiated or up-titrated to the next higher dose as per investigator's judgement; this change of treatment should be allowed to stabilize during the 14 days Screening Period. LTRAs treatment can be continued after End of Treatment (EOT) as per investigators decision.

Rescue medication such as SABAs will not be provided in this study, but may be prescribed by the investigator and used as needed.

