**Table 6-3 Prohibited medications**

Class of medication	Minimum cessation period prior to Treatment (Day 1)
Leukotriene receptor-Antagonists (LTRAs)	LTRAs should be stopped at Screening Visit (14 days), and in that case ICS should be up-titrated/initiated as per investigator's judgement and stabilized during the screening period.
Cyclosporine	6 months
Monoclonal antibodies, investigational or approved, for the treatment of asthma (e.g., omalizumab)	5 months
Oral corticosteroids	1 month
Any drug known to prolong QT interval	14 days or 5 half-lives, whichever is longer
Other investigational drugs	30 days or 5 half-lives, whichever is longer
Live attenuated vaccines	30 days
Rifampin, probenecid, ritonavir and valproic acid (i.e. medications blocking several pathways important for the elimination of QAW039 (broad range UGT inhibition and/or inhibition of OAT3, OATP1B3, MXR and P-gp))	7 days

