Assessment schedule, [Table 8-1](#) lists all of the assessments and indicates with an “X”, the visits when they are performed. All data obtained from these assessments must be supported in the subject's source documentation.

Period	Screening	Treatment 								Safety Follow-up
Visit Name	Screening	Treatment	End of Treatment						Follow-up 	
Days	up to -14	1	4 to 8						34 to 38	
Time (post-dose)	-	-	0h 	0.5h	1h	2h	3h	5h	8h	-
PK urine collection 				X						
Pregnancy and assessments of fertility	S	S	S 							
Electrocardiogram (ECG)	X		X 			X				
Dispense patient diary card		S								
Drug dispensation		S								
Adverse Events										X 
Asthma Exacerbation Episodes										X 
Serious Adverse Events										X 
Study drug administration at visit		X	X							
Record/interruption changes in study drug administrations to assess compliance		X	X 							
Record time of study drug taken one day prior to end of treatment			X							

Period	Screening	Treatment 							Safety Follow-up	
Visit Name	Screening	Treatment	End of Treatment						Follow-up 	
Days	up to -14	1	4 to 8						34 to 38	
Time (post-dose)	-	-	0h 	0.5h	1h	2h	3h	5h	8h	-
Disposition (Treatment/Study disposition)	X									
Reconcile study medication			S 							
Collect unused study medication			S 							
Collect patient diary card			S 							

X Assessment to be recorded in the clinical database or received electronically from a vendor

S Assessment to be recorded in the source documentation only

 Treatment visits may be conducted at the clinic or remotely at the subject's home. Ensure light breakfast is provided about 30 minutes prior to all doses from treatment day 1 to end of treatment (0h).

 Not a visit to site. Call Patient to collect the information on AE/SAE occurred within 30 days after last dosage

 0h refers to pre-dose

 These assessments should be conducted for patients who discontinue.

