## 9 Study discontinuation and completion

### 9.1 Discontinuation

#### 9.1.1 Discontinuation of study treatment

Discontinuation of study treatment for a subject occurs when study drug is stopped earlier than the protocol planned duration, and can be initiated by the subject, subject’s parent/legal guardian, or the investigator.

The investigator must discontinue study treatment for a given subject if, on balance, he/she believes that continuation would negatively impact the risk/benefit of trial participation.

Study treatment must be discontinued under the following circumstances:

- subject's or parent/legal guardian's wish
- Administration of a prohibited medication
- ECGs:
  - If the absolute QTcF  $\geq$  450 msec or an increase from baseline of  $>$  60 msec on 2 adequate ECGs at least a minute apart
  - 2nd or 3rd degree AV block
  - Atrial or ventricular arrhythmias (as judged clinically significant by the investigator)
- Any severe AE or SAE considered possibly related to the study medication
- Adverse events for which continuation of the study drug would be detrimental
- If a subject develops a medical condition that requires use of prohibited treatment as per [Section 6.2.2](#), or if subject exhibits a behavior of non-compliance regarding prohibited medications.
- Pregnancy (see [Section 10.1.4](#))
- Any situation in which study participation might result in a safety risk to the subject
- Clinically significant abnormal laboratory value(s) for children 6 to  $<$  12 years, as per the discretion of the physician
- Any other protocol deviation that results in a significant risk to the subject's safety

If discontinuation of study treatment occurs, the subject should NOT be considered withdrawn from the study. The subject should return to the clinic as soon as possible, after discontinuation of study drug, for a study treatment discontinuation visit (End of Treatment will act as an early discontinuation visit in this case) and directly move into the 30 day follow-up period. Treatment discontinuation visit assessments detailed in the [Table 8-1](#) should be completed and recorded in the eCRF. The investigator must determine the primary reason for the subject's premature discontinuation of study treatment and record this in the Study Disposition eCRF.

The investigator must contact the IRT to register the subject's discontinuation from study treatment.

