2.1.1.2 Baseline definition

For baseline assessments, checks will be performed to ensure the assessments were indeed taken prior to the first dose of study treatment. If baseline assessment (as mentioned in below

table) is missing or not confirmed to be pre-dose, the last value taken at any scheduled or unscheduled visit before the first administration of study treatment will be used for baseline. Otherwise, the baseline will be set to missing without imputation.

Parameter	Baseline assessment
Laboratory data (hematology, biochemistry)	Screening visit
Vital signs (body temperature, pulse rate, systolic and diastolic blood pressures)	Treatment Day 1 Pre-dose
Height, weight and BMI	Screening visit
ECG	Screening visit

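### For a child who stops a QT-prolonging drug at Screening, the SAP's QTcF baseline is recorded on that drug, so the change-from-baseline categories understate any rise

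*Protocol*

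**What the plan says.** **Eligibility.** Protocol 5.2, criterion 11, excludes a child "whose corrected QT interval (QTc) measured at Screening Visit (Fridericia method) is prolonged", with a limit of 450 msec. Criterion 12 admits a child on a Table 6-3 drug if the washout is completed before Day 1. For any drug known to prolong the QT interval, Table 6-3 requires "14 days or 5 half-lives, whichever is longer".

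**Screening.** Protocol Section 3 says of the Screening Visit: "At this visit, subjects will be instructed to withhold any prohibited medication as applicable". It adds: "The window between Screening Visit and Treatment Visit Day 1 (Screening Period) is up to 14 days".

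**ECG schedule.** Table 8-1 has ECGs at Screening, at End of Treatment (EOT) pre-dose and at EOT 2 h, and none on Day 1. The EOT pre-dose ECG is also marked for children who discontinue. The Day 1 eligibility check in Section 3 re-reads the existing ECG interpretation.

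**Baseline.** Protocol 12.2 uses the last measurement before the first dose. The table in SAP 2.1.1.2 names the Screening visit for ECG. The SAP turns to a later pre-dose value only if the Screening value is missing or not confirmed to be pre-dose. Its safeguard concerns timing against study drug only: "For baseline assessments, checks will be performed to ensure the assessments were indeed taken prior to the first dose of study treatment".

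**Use of the baseline.** Protocol 9.1.1 stops treatment on an absolute QTcF of at least "450 msec or an increase from baseline of" more than 60 msec. SAP 5.5 has two change categories, 30-60 and > 60 msec, and two absolute ones, > 450 and > 500 msec.

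**The concern.** The washout is counted back from Day 1, but the ECG is taken when the washout may only be starting. A child told at Screening to stop a QT-prolonging drug gives the baseline ECG on that drug and every later ECG off it. Loss of the old drug's effect is then subtracted from any effect of fevipiprant. The bias runs towards finding no QT effect.

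This matters because Protocol 1.2 describes these as the first safety data in this age group, and the cohorts are small enough for one child to be visible in a table of percentages. A site that took an extra ECG on Day 1 would not cure it in the analysis: a Screening ECG that is confirmed pre-dose remains the SAP baseline.

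**Working it through.** The plan states no figure to reproduce. The check has four steps.

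**1. Who can be affected.** Washout is the longer of 14 days and 5 half-lives, and screening lasts at most 14 days. A drug stopped at the Screening Visit meets the rule only if the full 14 days are used and 5 × half-life ≤ 14 days, so half-life ≤ 14/5 = 2.8 days. With a shorter screening period or a longer half-life, the drug must have been stopped before Screening. The Screening ECG then still falls inside the washout, but with a smaller residual effect.

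**2. Size of the bias.** Let q be the drug-free QTcF, d the msec added by the old drug at Screening, and r the true rise on fevipiprant. Both q and d are assumptions. Assume also that the old drug's effect has gone by the on-treatment ECG (5 half-lives leave 0.5^5, about 3%, of the drug).

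Reported change = (q + r) − (q + d) = r − d.

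| Assumed d (msec) | True rise needed for a reported 30 | True rise needed for a reported > 60 |
|---|---|---|
| 0 | 30 | > 60 |
| 5 | 35 | > 65 |
| 10 | 40 | > 70 |
| 20 | 50 | > 80 |
| 30 | 60 | > 90 |

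With d = 20, a true rise of 45 is reported as 25 and enters no category; a true rise of 70 is reported as 50 and falls in the 30-60 category.

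**3. Effect on the combined stopping rule.** The rule in 9.1.1 has two limbs joined by OR, and the absolute limb does not depend on baseline. The QTcF at which the rule is met is about min(q + 60, 450) with a drug-free baseline and min(q + d + 60, 450) with an on-drug one. The difference is what goes unseen:

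- q = 370: 430 becomes 435, 440, 450 and 450 for d = 5, 10, 20 and 30, so 5, 10, 20 and 20 msec are masked.
- q = 385: 445 becomes 450 for each of these d, so 5 msec are masked.
- q ≥ 390: q + 60 ≥ 450, so nothing is masked.

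**4. Where the two baseline definitions part.** If the Screening ECG is the only pre-dose ECG, Protocol 12.2 and SAP 2.1.1.2 pick the same recording. If a later pre-dose ECG exists, Protocol 12.2 picks the later one and the SAP keeps Screening. SAP Section 4 lists one change to the protocol analyses, the treatment-emergent window, and does not mention this.

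**Denominators.** The SAP introduction reports that Cohort A (6 planned) completed and that 5 Cohort B children were treated, none completing. One affected child would be 1/6 = 17% of Cohort A or 1/5 = 20% of treated Cohort B.

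**The case against.** The case for leaving this alone has real weight.

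- **Eligibility.** A reader might infer that a child with a prolonged QTc can slip in. The documents do not support that. A QT-prolonging drug raises the Screening value, so criterion 11 may wrongly exclude a child but would not admit one whose drug-free QTcF is 450 msec or more.
- **Stopping rule.** A reader might infer that the rule as a whole moves to 70-90 msec. It does not: step 3 shows the cap set by the absolute limb. The scheduled on-treatment ECGs also fall on the last dosing day, so at most the final dose could be withheld.
- **Absolute categories.** The > 450 and > 500 msec counts do not move, because an eligible child starts below 450 msec.
- **Numbers affected.** The group is narrow, nothing in the documents shows that any child was in it, and the study has ended. Changes to the protocol can no longer alter these data.
- **Listings.** SAP 2.4.2 lists prior and concomitant medications and SAP 2.6.1.3 lists all ECG data, so a reader could match 11 children by hand.

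The first four points stand, and they limit the issue to the reported change categories. The last stands only in part: the listings hold the information, but the tabulated category for an affected child would still be wrong and nothing would mark it.

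**Conclusion.** The concern holds as a matter of baseline definition and reporting. For any child whose Screening ECG was recorded on a QT-prolonging drug that was then washed out, the QTcF change is understated by d msec, and the 30-60 and > 60 msec categories shift by the same amount. The SAP would do this even with a usable post-washout ECG on file, contrary to Protocol 12.2.

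The size rests on d, which the documents do not give; 5 to 30 msec is an illustrative range. It also rests on at least one child having stopped such a drug at or shortly before Screening, and that number may be zero among the 11 treated. It is nevertheless worth correcting, because the cohorts are small, the bias is towards no effect, and the correction costs almost nothing.

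**What to change.** **In the SAP (the action that still matters):**

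- In 2.1.1.2, define the ECG baseline as the last ECG before the first dose, in line with Protocol 12.2.
- Check prior and concomitant medication dates against Screening ECG dates. Flag any child whose Screening ECG fell inside the Table 6-3 washout for a QT-prolonging drug, and show that child's QTcF change separately. If there were none, say so in one sentence.

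The flag is needed as well as the new definition, because a child with no later pre-dose ECG keeps the Screening value under either wording. The cost is a wording change and a date check in 11 children, using data the SAP already plans to list.

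**For any further use of the design:** reconcile criteria 11 and 12 with Table 8-1 so that, in a child who washes out such a drug, the baseline ECG is recorded after washout and before the first dose. The cost is at most one re-timed or repeated 12-lead ECG in those few children.

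No change to any QTc threshold, washout period or stopping rule is proposed.
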